#### Section 1: Administrative information

1a: The title of the project is "Presence of the partner in the operating room during hyperacute cesarean section in general anesthesia" (in Danish: Sectio grad 1. Partneren med på operationsstuen?)

1b: The trial protocol is registered at clinicaltrials.gov (NCT04948892). Since there is no intervention in the trial, approval from the Research Ethics Committee was not required. The trial is approved by the Research Ethis Committee of the University of Southern Denmark (approval 21/62092, November 19., 2021). The study is approved by the Data Management authority of the Region of Southern Denmark (file number 21/56789, October 25., 2021).

- 2: SAP version 1.1
- 3: Referring to the trial protocol per November 1st, 2021.
- 4: NA
- 5: The statistical analysis plan is developed by:

[name] [name], postdoc, department of anesthesiology and intensive care, University Hospital of Southern Denmark, Kolding (responsible for the trial), and

[name], biostatistician, University Hospital of Southern Denmark, Kolding (senior statistician responsible)

And approved by the rest of the trial investigators.

#### Section 2: Introduction

#### 7: Synopsis of trial background and rationale

This study concerns cesarean sections, category 1, meaning those cases where the life of mother and/or fetus is in immediate danger and the child must be delivered within 15 minutes from activating the cesarean section team. In most hospitals in Denmark, these cesarean sections are most often performed in general anesthesia and the mother is endotracheally intubated.

Previously in these situations, as the mother was rushed from the Labour Ward to the operation room (OR), her spouse/partner, would be placed outside the OR, and would stay there until the child had been delivered.

In Lillebaelt Hospital, Kolding, Denmark, the newborn-resuscitation table is placed inside the OR. The partner would most often be allowed to enter the OR when the child was delivered and placed on the resuscitation table (no matter the status of the child). However, during 2021, Lillebaelt Hospital Kolding updated the policy regarding the handling of the partner during cesarean section category 1 (implemented in the local guideline December 2021). Now the partner is present in the OR during the whole procedure, including the induction of general anesthesia, endotracheal intubation, performing the cesarean section (drapings are positioned so that the partner cannot see the operation field) and potential resuscitation efforts of the newborn.

In another hospital in the same region (Region of Southern Denmark), Aabenraa Hospital, the partner is not present in the OR during the cesarean section category 1. The partner waits in the labour ward.

The investigators therefore wish to investigate how the cesarean section category 1 is experienced by: the partner; the mother; the obstetrician; the anesthesiologist; the midwife; the OR nurse; the anesthetic nurse, both in Kolding where the partner is present in the OR, and in Aabenraa, where the partner is not present in the OR during the cesarean sectio.

In 2020 there were 16 cesarean sections category 1 in Kolding and 15 in Aabenraa.

8: Description of specific objectives or hypotheses

We hypothesize the mothers and partners will prefer the partner being present in the OR during the cesarean section category 1.

#### Sectio 3: Study methods

- 9: Trial design: This is prospective cohort trial with two parallel cohorts in two centers (Kolding and Aabenraa).
- 10: Randomization: This is a non-randomized trial.
- 11: Sample size: The trial is based on a convenience sample consisting of all the cesarean sections in 2022 in each of the two participating centers.
- 12: Framework: This is an exploratory trial without statistical power to perform superiority, equivalence, or noninferiority hypothesis testing.
- 13: Statistical interim analyses: NA

14: Timing of final analysis: All analyses will be conducted when the inclusion period has ended (January 1st 2023).

15: Timing of outcome assessments: outcomes will be assessed for each cesarean section (first questionnaire in day 1 or 2 following the cesarean section, follow-up interview three months later). Data on outcomes will be analyzed when the inclusion period has ended.

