### Section 4: Statistical Principles

16: Level of statistical significance: a p-value of <0.05 will be considered significant. However, due to the expected low number of cases (expected approx. 15 cesarean section category 1/year in each center), it is likely that descriptive statistics will be most appropriate.

- 17: Description and rationale for any adjustment for multiplicity: NA
- 18: Confidence intervals to be reported: see 16.

19a: Definition of adherence to the intervention: for each cesarean section is will be described whether or not the partner was present in the operation room during the cesarean section.

19b: Description of how adherence to the intervention will be presented: the information will be available in the result section in the final manuscript.

19c: Definition of protocol deviations for the trial: for various reasons the partner may or may not be present in the OR even though he/she was supposed to or supposed not to; there might not be a partner, the partner could be ill or otherwise occupied etc.

19d: Description of which protocol deviations will be summarized: in tabular form in the result section in the final manuscript.

20: Definition of analysis populations, eg, intention to treat, per protocol, complete case, safety: We will perform intention-to-treat analyses. However, as the trial aims to explore the situation of having the partner present in the OR versus not having the partner present, we will also assess data per protocol, if it turns out that there are multiple cases of protocol deviations. This will be done using descriptive statistics, and without statistical tests.

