## Section 5: Trial Population

- 21: Screening data: We have not collected screening data but planned for a convenience sample of one year inclusion period.
- 22: Summary of eligibility criteria: All cesarean section category 1 in 2022 are eligible and mother and partners will be approached for consent to participate.
- 23: Information to be included in the CONSORT flow diagram: see template for Consort flow diagram for the trial.

24a: Level of withdrawal, eg, from intervention and/or from follow-up: We expect that 20% of the mothers and partners will decline to participate. We expect that >90% of partners, who accept to participate, will also participate in the follow-up interview.

24b: Timing of withdrawal/lost to follow-up data: NA

24c: Reasons and details of how withdrawal/lost to follow-up data will be presented: Data will be presented in the result section of the final manuscript.

25a and b: Baseline patient characteristics:

Table 1. Baseline data

	Kolding	Aabenraa
	n=	n=
Age of mother		
BMI, mother		
ASA score, mother		
Parity, mother		
Partner was present during		
cesarean section		
Age of partner		
Indication for cesarean section		
-fetal distress		
-bleeding		
-uterus rupture		
-other		
Time from calling the cesarean		
section till infant is delivered		
Bleeding, ml		
Need for blood transfusion		
APGAR scores		
-1 min		
-5 min		
-10 min		
Surgical complications		
-bladder perforation		
-bowel perforation		
-bleeding>1000 ml		
Anestesiological complications		
-difficult airway		
-esophageal intubation		
-aspiration		
Time from cesarean section to		
discharge from hospital		
Postoperative infection		
Need for repeat surgery		
Additional clinically relevant		
information from each cesarean		
section		

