# Section 6: Analysis

#### 26: Outcome definitions

The primary outome will be the partners answer to the main study question: "Would you have preferred to wait outside the OR during the anesthesia and cesarean section?" for partners in Kolding and "Would you have preferred to be present in the OR during the anesthesia and cesarean section?" for partners in Aabenraa. This question is asked both at first interview (day 1 or 2 following the cesarean section) and at follow-up three months later. The number of partners answering "yes" will be shown in number and percentages, n (%).

Secondary outcomes will be narrative and tabular descriptions of questionnaire data from mothers, medical data regarding the cesarean section and infant, follow-up interviews and questionnaires from health care professionals.

27: Analysis methods: Descriptive statistics will be used where appropriate.

As cesarean section category 1 is usually performed by a smaller group of specialized clinicians, it is likely that the same clinicians will perform several of the cesarean sections in this study. As part of the analyses, data will be investigated for clinician-specific effects by including the clinician as a random effect in a mixed effect model and investigate the varians components. If there should be clinicial specific effects, against what we expect, the statistical analyses will include the found cluster structure and analyse as non-independent data.

28: Missing data: We will present the extent of missing data. No form of imputations for missing data will be used.

29: Additional analyses: None planned.

30: Harms: NA, as this is an observational study, describing the existing practice in two different hospitals.

31: Statistical software: STATA will be used.

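### Items 14 and 15 time all analyses from the end of inclusion (1 January 2023), not from the last three-month follow-up; read literally, about 5 of about 22 three-month primary answers would not yet exist

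*SAP*

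**What the plan says.** Two items in the SAP's section on study methods set the time of analysis. Item 14, whose subject is the final analysis, says "All analyses will be conducted when the inclusion period has ended" and adds the date 1 January 2023 in brackets. Item 15 first describes the assessments ("first questionnaire in day 1 or 2 following the cesarean section, follow-up interview three months later") and then closes with "Data on outcomes will be analyzed when the inclusion period has ended". Item 13 reads "Statistical interim analyses: NA".

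Three other items determine what data will exist at that point:

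- **Eligibility (item 22):** "All cesarean section category 1 in 2022 are eligible and mother and partners will be approached for consent to participate". Inclusion therefore runs to 31 December 2022.
- **Primary outcome (item 26):** the partner's answer to the main study question, reported as a number and percentage. "This question is asked both at first interview (day 1 or 2 following the cesarean section) and at follow-up three months later".
- **Expected follow-up (item 24a):** "We expect that >90% of partners, who accept to participate, will also participate in the follow-up interview".

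No item links the analysis, or closure of the data, to the last three-month interview. Item 24b, on the timing of loss to follow-up, is marked not applicable.

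**The concern.** The end of inclusion is the right milestone only for an outcome known at inclusion or within a day or two of it. Here one of the two primary time points comes three months later. A partner whose section took place in the last quarter of 2022 cannot have given the three-month answer by 1 January 2023. Item 15 makes this more than a slip in one place, because it names the three-month interview and then still gives the end of inclusion as the trigger.

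If the rule were followed literally, the three-month primary result would be tabulated without about the last quarter's partners. In so small a study each answer carries visible weight in the percentage. Item 28 reports the extent of missing data without imputation, and the SAP has no rule separating an interview not yet due from one refused or lost, so pending answers could be reported as missing. Because item 13 plans no interim analysis, the SAP also has no label for a result produced before follow-up is complete.

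**Working it through.** The SAP states no expected number of three-month answers, so there is no figure of its own to reproduce. The check builds one from the SAP's stated expectations.

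**Inputs**

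| Input | Value | Source |
|---|---|---|
| Sections per centre and year | about 15 ("expected approx. 15 cesarean section category 1/year in each center") | item 16 |
| Centres | 2 | item 9 |
| Decline to participate | 20% | item 24a |
| Partners followed up, of those accepting | above 90%; 90% used as lower bound | item 24a |
| Inclusion | calendar year 2022, 365 days | items 11 and 22 |
| Follow-up | three months after the section | items 15 and 26 |
| Spread of sections over the year | even | assumption; the SAP gives no monthly figures |

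**Step 1: expected three-month answers.** 2 × 15 = 30 sections. 30 × 0.80 = 24 consenting partners. 24 × 0.90 = 21.6 answers, or 10.8 per centre.

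**Step 2: share of inclusion days not yet at three months.** Counting three months as 90, 91 or 92 days or as calendar months, 89 to 91 days of 2022 have a three-month date after 1 January 2023, and 90 to 92 days have one on or after it. That is 24% to 25% of 365. The first affected section falls between 1 and 4 October 2022. A section on 31 December 2022 is due about 31 March 2023.

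**Step 3: answers not yet in existence.** 21.6 × 91/365 = 5.4, or 2.7 per centre. Left: 21.6 − 5.4 = 16.2, or 8.1 per centre.

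**Step 4: range.**

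- Chance variation in timing, Binomial(22, 91/365): the 2.5% and 97.5% quantiles are 2 and 10.
- Uneven accrual: with 15% of sections in the last quarter, 21.6 × 0.15 = 3.2; with 35%, 21.6 × 0.35 = 7.6.
- Full follow-up instead of 90%: 24 × 92/365 = 6.0 of 24.
- The 2020 counts in item 7 (16 + 15 = 31 sections): 31 × 0.80 × 0.90 = 22.3 answers, of which 22.3 × 92/365 = 5.6 are outstanding.

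**Step 5: effect on the reported percentage.** One answer is worth 1/10.8 = 9.3 percentage points per centre with complete follow-up, and 1/8.1 = 12.3 points at the literal analysis date.

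**Step 6: comparison with item 24a.** By 1 January 2023 only (365 − 91)/365 = 75% of partners would have reached three months. With 90% participation, 16.2/24 = 68% would have answered. The expected follow-up above 90% cannot be met on that date even if every partner takes part when due.

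**Step 7: the day 1-2 answer.** Only a section on 31 December 2022 has its day 2 after 1 January 2023: 24 × 1/365 = 0.07 answers. Counting 30 December as well gives 24 × 2/365 = 0.13. Either way it is about 0.1 of 24.

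**The case against.** The strongest reply is that the literal reading is not what the authors mean. The bracketed date follows the words about inclusion and can date that event only, in which case it sets an earliest point for analysis and no cut-off. Item 15 says outcomes are assessed for each section, December included, and its last sentence may serve only to rule out looking at data during accrual. Item 24a expects follow-up above 90%, which is impossible on 1 January 2023 (step 6), and the absence of interim analyses suggests a single analysis of complete data. The study is also exploratory and descriptive, no decision hangs on the timing, and item 28 would make missing answers visible.

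Much of this stands. Complete follow-up is probably intended, and on that reading no answer is lost; the count of about 5 is conditional on following the text as written. What the reply does not supply is a sentence that makes the analysis wait. If the trigger is only an earliest point, item 14 leaves the time of the final analysis open, although fixing it is that item's purpose. If it is the actual time, it conflicts with items 24a and 26. Both readings call for the same correction. Nor is this a detail left to the protocol, which is not at hand: the SAP states a trigger itself, twice, and it does not fit its own primary time point.

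**Conclusion.** The point holds as a rule that names the wrong milestone, and it should be fixed. Its weight is modest. Read literally, about 5.4 of 21.6 expected three-month primary answers would be absent from the analysis, with a chance range of about 2 to 10, and 3.2 to 7.6 if the last quarter held 15% to 35% of sections. The size rests on the SAP's own expectations for case numbers, consent and follow-up, and on the assumption of even accrual over 2022. The consequence is confined to the three-month time point; the day 1-2 primary answer is essentially complete on either reading. No direction of bias is claimed, since nothing in the SAP suggests that partners from late 2022 would answer differently.

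**What to change.** Reword items 14 and 15 so that the final analysis is done once, after the last included partner has completed the three-month follow-up or has passed the window for it. With inclusion to 31 December 2022 this means about early April 2023 plus the contact window. Add that any earlier report is limited to the day 1-2 answer and labelled as such.

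The cost is one sentence in each item. The final analysis moves about three months later than a literal reading of the SAP, with no extra participants and no extra data.

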### Section 4: Statistical Principles

16: Level of statistical significance: a p-value of <0.05 will be considered significant. However, due to the expected low number of cases (expected approx. 15 cesarean section category 1/year in each center), it is likely that descriptive statistics will be most appropriate.

- 17: Description and rationale for any adjustment for multiplicity: NA
- 18: Confidence intervals to be reported: see 16.

19a: Definition of adherence to the intervention: for each cesarean section is will be described whether or not the partner was present in the operation room during the cesarean section.

19b: Description of how adherence to the intervention will be presented: the information will be available in the result section in the final manuscript.

19c: Definition of protocol deviations for the trial: for various reasons the partner may or may not be present in the OR even though he/she was supposed to or supposed not to; there might not be a partner, the partner could be ill or otherwise occupied etc.

19d: Description of which protocol deviations will be summarized: in tabular form in the result section in the final manuscript.

20: Definition of analysis populations, eg, intention to treat, per protocol, complete case, safety: We will perform intention-to-treat analyses. However, as the trial aims to explore the situation of having the partner present in the OR versus not having the partner present, we will also assess data per protocol, if it turns out that there are multiple cases of protocol deviations. This will be done using descriptive statistics, and without statistical tests.

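### Must the SAP fix a confidence interval for the primary percentages, when item 18 only points to item 16?

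*SAP*

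**What the plan says.** Item 18 of Section 4 reads "Confidence intervals to be reported: see 16". Item 16 states that "a p-value of <0.05 will be considered significant", then qualifies this: with few cases ("expected approx. 15 cesarean section category 1/year in each center"), description will probably serve better than testing. It mentions no interval.

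Item 26 (Section 6) defines the primary outcome as the partner's yes/no answer to one question, asked on day 1 or 2 and again at three months. The question is worded in opposite directions in the two centres. The result is the number answering yes, with a percentage. Item 27 plans descriptive statistics. It adds that, if clinician-specific effects are found, the analysis will take that clustering into account.

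Two further items set the frame. Item 12 (Section 3) says "This is an exploratory trial without statistical power to perform superiority, equivalence, or noninferiority hypothesis testing". Item 8 (Section 2) gives a directional expectation: "We hypothesize the mothers and partners will prefer the partner being present in the OR".

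**The concern.** The plan has an item for confidence intervals, and its answer leads to text that contains none. The cross-reference can be read in two ways: intervals at the level matching 0.05, or description only and no intervals. Two analysts could follow the plan and report different things.

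The numbers make this look important. With about a dozen partners per centre, a bare percentage conveys little about its own precision. In Kolding a yes means the partner would rather have waited outside, so the hypothesis in item 8 predicts few yes answers and zero is a plausible count. A reader might take 0 (0%) as proof that no partner would prefer to wait outside, which a sample of that size cannot show. Lack of power is no reason to omit an interval either, since an interval for a single proportion needs no test.

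**Working it through.** The SAP gives no interval or sample-size calculation to reproduce, so the check derives the expected numbers and then the intervals.

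**Inputs**
- Cases per centre: about 15 a year (item 16); in 2020, 16 in Kolding and 15 in Aabenraa (item 7).
- Refusal: "We expect that 20% of the mothers and partners will decline to participate" (item 24a).
- Follow-up: more than 90% "of partners, who accept to participate, will also participate in the follow-up interview" (item 24a).
- Assumptions: one partner per section, and a 95% level taken from the 0.05 in item 16.

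**Expected partners per centre**
- First interview: 15 × 0.8 = 12; 16 × 0.8 = 12.8.
- Three months: 12 × 0.9 = 10.8; 12.8 × 0.9 = 11.5. As the SAP expects more than 90%, these are lower limits.
- Item 19c notes that "there might not be a partner", which would lower n, but the SAP gives no rate.

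**Exact (Clopper-Pearson) 95% interval for x of n**
- Lower limit: 0.025 quantile of Beta(x, n − x + 1), or 0 if x = 0.
- Upper limit: 0.975 quantile of Beta(x + 1, n − x), or 1 if x = n.
- For x = 0 the upper limit is 1 − 0.025^(1/n). At n = 12 this is 1 − 0.735 = 0.265.

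| n | narrowest width (x = 0 or n) | widest width (x near n/2) |
|---|---|---|
| 13 | 24.7 points | 55.6 points |
| 12 | 26.5 points | 57.8 points |
| 11 | 28.5 points | 59.9 points |
| 10 (if some sections have no partner) | 30.8 points | 62.6 points |

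Illustrative counts at n = 12: 0/12 gives 0 to 26.5%; 3/12 (25%) gives 5.5 to 57.2%; 9/12 (75%) gives 42.8 to 94.5%. Wilson intervals at n = 12 are 24.2 to 49.2 points wide, so the choice of method does not alter the picture.

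**What would differ if an interval were fixed in the plan**
1. *The estimate.* Nothing. The count and percentage are correct as planned.
2. *A decision.* Nothing. Item 8 sets no threshold against which an interval would be judged, and item 26 plans no comparison between centres.
3. *What the reader can learn.* Very little. The interval above is a function of x and n alone, and the count and percentage together give both.
4. *Consistency with the rest of the SAP.* A possible loss. The exact interval assumes independent answers. Item 27 says that clustering by clinician, if found, will be carried into the analysis. A fixed independent-data interval would then be too narrow and would conflict with that rule.

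**The case for a change.** The strongest case for a change is that a plan with a dedicated item should answer it. If the authors want no intervals, item 18 should say so; if they want them, it should give level and method. The remedy costs a sentence and one command per centre and time point. A small sample is also where an interval is most useful, and the study is a convenience sample with expected refusals, so it cannot be excused as a complete census.

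Much of this stands. The cross-reference is loose, the widths are large, and an interval would be good practice in the final report. What does not follow is that the plan is wrong without it. Items 12, 16, 26 and 27 all describe a small descriptive study and do not contradict one another on the primary outcome. The 0.05 threshold in item 16 is qualified in its next sentence on the same ground as item 12, so it does not commit the authors to testing the primary outcome. Either reading of item 18 gives an acceptable report: a count and percentage alone, or the same with a 95% interval. An interval would also cover random error only, not the selection that 20% refusal may bring, so it would not show all the uncertainty in these percentages.

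**Conclusion.** The observation is accurate, but it concerns reporting detail and needs no change to the plan. Item 18 does lead to an item that names no interval. At about 12 to 13 partners per centre (about 11 or more at three months), a 95% exact interval would be roughly 25 to 60 points wide. Those sizes rest on the SAP's own case, refusal and follow-up expectations, one partner per section, independent answers and a 95% level.

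Following the plan as written gives a correct result with its count shown, in a study that openly disclaims power. No conclusion, comparison or decision turns on the missing interval. Analysts who choose to add one have a natural level in item 16 and a rule for clustering in item 27, and nothing in the SAP prevents them. Fixing an independent-data interval now would add little and could conflict with item 27.

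### Does item 20 need an unconditional, fully defined per-protocol table when partners deviate from their hospital's practice?

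*SAP*

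**What the plan says.** Section 4, item 20 sets out the populations: "We will perform intention-to-treat analyses. However, as the trial aims to explore the situation of having the partner present in the OR versus" the partner's absence. For that reason it adds a second, conditional look: "we will also assess data per protocol, if it turns out that there are multiple cases of protocol deviations", with the limit "This will be done using descriptive statistics, and without statistical tests".

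Item 19a commits to describing, for each section, "whether or not the partner was present in the operation room during the cesarean section". Item 19c defines a deviation as presence or absence contrary to what was intended, and gives as possible reasons that "there might not be a partner, the partner could be ill or otherwise occupied etc". Item 19d tabulates the deviations, and Table 1 (Section 5) has a row for partner presence by hospital.

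Section 6, item 26 defines the primary outcome by hospital. Kolding partners are asked whether they would rather have waited outside, Aabenraa partners whether they would rather have been inside. The number and percentage of yes answers are reported. Section 3, item 10 states the design: "This is a non-randomized trial".

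**The concern.** Item 8 in Section 2 frames the hypothesis around presence itself: "We hypothesize the mothers and partners will prefer the partner being present in the OR during the cesarean section category 1". Item 20 likewise gives presence versus absence as the aim. Yet the unconditional analysis groups partners by hospital, and the look that takes actual presence into account depends on an unquantified word. Four things seem loose.

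- The trigger depends on the data and has no threshold, so whether the look happens could be settled once the answers are known.
- The trigger may count the wrong events. A section with no partner is a deviation under item 19c but yields no answer to the primary question. One partner who deviated and did answer would not make the deviations several.
- Per protocol could mean removing deviating partners or regrouping them by actual presence.
- If they were regrouped, the opposite questions in item 26 would need a coding rule, and none is written.

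At stake is whether a reader can see how deviating partners answered. In groups this small, one answer moves a percentage visibly.

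**Working it through.** **Inputs.** Item 16 gives the number of sections: "expected approx. 15 cesarean section category 1/year in each center". Item 24a expects 20% of mothers and partners to decline and more than 90% of participating partners to take part in the follow-up interview. The SAP gives no deviation rate and no expected share of yes answers, so those below are assumptions. It states no power or sample-size figure to reproduce.

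**Partners answering.** 15 × (1 − 0.20) = 12 per hospital, 24 in all. At three months, 12 × 0.90 = 10.8, about 11 per hospital.

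**Weight of one deviating partner.** At most 1/12 = 8.3 points of a hospital's percentage, and 1/11 = 9.1 points at three months. These are ceilings. As a milder illustration, take 11 Kolding partners who were present, 2 of whom say yes, and one who was outside. By hospital the figure is 2/12 = 16.7% or 3/12 = 25.0%, depending on that one answer. Without that partner it is 2/11 = 18.2%. The shift is 1.5 or 6.8 points.

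**How often the condition matters.** With n units and deviation rate p, P(exactly one) = n·p·(1 − p)^(n−1). The base is 24 answering partners, or about 30 sections (2 × 15) if deviations are counted per section as in item 19a.

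| Assumed p | Exactly 1 of 24 | Exactly 1 of 30 | At least 2 of 24 | At least 3 of 24 |
|---|---|---|---|---|
| 2% | 0.30 | 0.33 | 0.08 | 0.01 |
| 5% | 0.37 | 0.34 | 0.34 | 0.12 |
| 10% | 0.21 | 0.14 | 0.71 | 0.44 |
| 20% | 0.03 | 0.01 | 0.97 | 0.89 |

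If the trigger is read in its ordinary sense as two or more, the look is lost only when there is exactly one deviation, and the 8.3-point ceiling applies. If it were read as three or more, two deviations in the same hospital could also go unexamined, with a ceiling of 2/12 = 16.7 points.

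**Imprecision for comparison.** The exact (Clopper-Pearson) 95% interval for 2 of 12 is 2.1% to 48.4%, a width of 46.3 points. Either ceiling is small beside it.

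**Leaving out versus regrouping.** Suppose 8 of 12 Aabenraa partners prefer to be present, and one Kolding partner who was outside prefers outside. Leaving that partner out gives 8/12 = 66.7% preferring presence in the absent group. Regrouping gives 8/13 = 61.5%, a difference of 5.1 points. The coding question arises only on the second route. If deviators are left out, everyone remaining in a group answered the same item 26 question.

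**The case for a change.** The strongest case for a change is that an item meant to define analysis populations leaves one undefined. With about 24 partners, whoever settles the definition will have seen individual answers. The reason item 20 gives for the look, presence versus absence, points to grouping by actual presence as much as to exclusion. Item 29 plans no other analysis that would fill the gap. Presence is recorded anyway, so an always-shown table would cost little.

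The textual part stands: the threshold is not stated, the per-protocol set is not spelled out, and sections without a partner fit awkwardly among the deviations. The rest carries less weight.

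- Regrouping by actual presence is usually called as-treated, a term the SAP does not use. The default reading of per protocol is therefore exclusion.
- By-presence groups would be partly self-selected through the reasons for absence in item 19c.
- Regrouping would place answers to opposite questions side by side. A Kolding partner who was outside is asked about preferring to wait outside, and it is unclear whether a no there means a wish to be inside or no stated preference.
- With a single deviation, showing that partner's answer separately risks identifying a person, since presence is tabulated by hospital.
- The narrative and tabular description of follow-up interviews in item 26 may bring out such answers, although the SAP does not promise this.

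**Conclusion.** No change to the plan is needed. Item 20 leaves a threshold and a definition unstated, but the plan followed as written still supports a sound descriptive conclusion. The by-hospital comparison is a legitimate description of two practices, which is how Section 2 and item 30 present the study. When several partners deviate, the extra look is already planned. It carries no tests, so a data-dependent trigger puts no error rate at risk.

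The gain from an unconditional table is confined, on the ordinary reading of the trigger, to the case of exactly one deviation. It is bounded by 8.3 points at the first interview and 9.1 at three months, against an interval more than 46 points wide. Compulsory regrouping would be a debatable trade-off, because it brings the coding and identification problems with it.

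This rests on 12 answering partners per hospital, on assumed deviation rates of 2% to 20%, on reading the trigger as two or more, and on per protocol meaning exclusion. Analysts can be expected to adopt those readings and to count sections without a partner only among the deviations of item 19d.
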